## **5.7 EXPEDITED REPORTING TO HEALTH AUTHORITIES, INVESTIGATORS, INSTITUTIONAL REVIEW BOARDS, AND ETHICS COMMITTEES**

The Sponsor will promptly evaluate all serious adverse events and adverse events of special interest against cumulative product experience to identify and expeditiously communicate possible new safety findings to investigators, IRBs, ECs, and applicable health authorities based on applicable legislation.

To determine reporting requirements for single adverse event cases, the Sponsor will assess the expectedness of these events using the following reference documents:

- Atezolizumab Investigator's Brochure
- Local prescribing information for enzalutamide

The Sponsor will compare the severity of each event and the cumulative event frequency reported for the study with the severity and frequency reported in the applicable reference document.

Reporting requirements will also be based on the investigator's assessment of causality and seriousness, with allowance for upgrading by the Sponsor as needed.

## **6. STATISTICAL CONSIDERATIONS AND ANALYSIS PLAN**

Analysis populations are defined as follows:

- The intent-to-treat (ITT) population is defined as all randomized patients regardless of whether the assigned study treatment was received. For efficacy analyses, patients will be analyzed according to their randomized treatment assignment.
- Objective response rate in soft tissue lesions will be analyzed in patients in the ITT population with measurable soft tissue lesions at baseline.
- The duration of response (DOR)-evaluable population is defined as patients with an objective response in soft tissue lesions.
- The safety population is defined as patients who received any amount of any component of the study treatments (atezolizumab, or enzalutamide). Patients will be allocated to treatment arms according to the treatment they actually received (i.e., patients randomized to enzalutamide alone who received at least one full or partial dose of atezolizumab will be included in the atezolizumab arm for safety).

Safety run-in patients are not included in the populations defined above. Safety and efficacy data from these patients will be presented separately.

Baseline measurements are the last available data obtained prior to the patient receiving the first dose of study treatment.

### **6.1 DETERMINATION OF SAMPLE SIZE**

A total of approximately 730 patients are planned to be enrolled in the global phase of this study: 10 patients during the non-randomized safety run-in phase, and approximately 720 during the randomized phase of the study.

The sample size of 10 patients for the safety run-in is based on clinical considerations. No statistical hypothesis tests will be performed on data from the safety run-in phase.

The final analysis of the primary endpoint of OS will be performed when approximately 540 deaths have occurred in the ITT population (75% of 720 patients).

The calculations are based on the following assumptions:

- Log-rank test
- 1:1 randomization
- Two-sided alpha of 0.05
- Median OS for the control (enzalutamide alone) arm of 12 months and estimated median OS in the experimental arm of 16.7 months, corresponding to a HR of 0.72
- A drop-out rate of approximately 5% per 2-year period
- One interim OS analysis

It is projected that an observed HR of  $\leq 0.84$  will result in a statistically significant difference between treatment arms (i.e., the HR of 0.84 will be the minimally detectable difference at the final analysis). This corresponds to an improvement of median OS from 12 months to 14.3 months.

In case of proportional hazards, 540 events would provide 97% power to detect a difference in the duration of OS given the above assumptions. However, computer simulations show that the actual power of the log-rank test is likely lower in case of control patients switching to subsequent lines of immunotherapy following progression. For example, if 15% of control patients receive subsequent treatment providing similar OS benefit as atezolizumab, the reduction in power is projected to be approximately 6%.

Recruitment of the planned 720 patients is projected to be completed within 13 months. On the basis of the above assumptions, the required number of OS events for the final analysis is projected to occur at approximately Month 38 after randomizing the first patient.

## **6.2 SUMMARIES OF CONDUCT OF STUDY**

Enrollment and reasons for discontinuation from the study will be summarized by treatment arm for the ITT population. Major protocol deviations, including major deviations of inclusion and/or exclusion criteria, will be summarized by treatment arm for the ITT population. Study treatment administration and reasons for discontinuation from study treatment will be summarized.

## **6.3 SUMMARIES OF DEMOGRAPHIC AND BASELINE CHARACTERISTICS**

Demographic characteristics, such as age, sex, race/ethnicity, baseline disease characteristics, etc., will be summarized by treatment arm for the ITT population. Continuous variables will be summarized using means, standard deviations, medians, and ranges. Categorical variables will be summarized by frequencies and percentages.

## **6.4 EFFICACY ANALYSES**

### **6.4.1 Primary Efficacy Endpoint**

The primary efficacy endpoint is OS, defined as the time from randomization to death from any cause. Data for patients who are not reported as having died at the date of analysis will be censored at the last date known to be alive. Data for patients who do not have post-baseline information will be censored at the date of randomization plus 1 day.

The primary comparison of OS between treatment arms will be based on a stratified log-rank test. The HR for death in the experimental arm compared with the control arm will be estimated using a stratified Cox regression model, and the 95% CI will be provided. The stratification factors will be the same as the randomization stratification factors; however, stratification factors may be combined for analysis purposes if

necessary to minimize small stratum cell sizes. Combination of stratification factors, if any, would be specified in the SAP prior to analysis. Values for the stratification factors will be as recorded in the IxRS at the time of randomization. Results from an unstratified analysis will also be presented.

Kaplan-Meier plots will be constructed to provide a visual description of the difference between the treatment and control arms. Kaplan-Meier methodology will also be used to estimate median OS for each treatment arm. Brookmeyer-Crowley methodology will be used to construct the 95% CI for the median OS for each treatment arm.

The OS rate at key timepoints (12 months, 24 months) will be estimated using Kaplan-Meier methodology, along with 95% CIs calculated using the standard error derived from Greenwood's formula. The 95% CI for the difference in OS rates between the two treatment arms will be estimated by use of the normal approximation method.

#### **6.4.2            Secondary Efficacy Endpoints**

Analyses of the primary endpoint of OS and the key secondary efficacy endpoints listed below will be performed in a hierarchical fashion with type 1 error control (see Section 6.8.1). The primary endpoint of OS will be analyzed first. If the null hypothesis for the OS endpoint is rejected, then the key secondary endpoints will be in the order provided:

1. Time to cancer-related pain progression
2. Time to first symptomatic skeletal event (SSE)
3. rPFS

If for one endpoint in this list the null hypothesis cannot be rejected, then the results for this and all following endpoints are not considered to be statistically significant. Analyses of other secondary endpoints of this study will be considered as descriptive in nature, and no formal hypothesis testing will be conducted.

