
 
To evaluate the efficacy of atezolizumab/enzalutamide compared with enzalutamide alone
 
	
 
OS probability at 12 and 24 months
 
Time to first SSE               
An SSE is defined as external beam radiation therapy to relieve skeletal symptoms (including initiation of radium-223 dichloride or other types of radionuclide therapy to treat symptoms of bone metastases), new symptomatic pathologic bone fracture, clinically apparent occurrence of spinal cord compression, or tumor related orthopedic surgical intervention.
 
 
rPFS, as assessed by the investigator, and adapted from the PCWG3 criteria. rPFS is defined as the time from randomization to the earliest occurrence of one of the following:               
A patient is considered to have progressed by bone scan if:
 
The first bone scan with <math>\geq 2</math> new lesions compared to baseline is observed <math>< 12</math> weeks from randomization and is confirmed by a second bone scan taken <math>\geq 6</math> weeks later showing <math>\geq 2</math> additional new lesions (a total of <math>\geq 4</math> new lesions compared to baseline); the date of progression is the date of the first post-treatment scan, OR
 
After the first post-treatment scan, <math>\geq 2</math> new lesions are observed relative to the first post-treatment scan, which is confirmed on a subsequent scan <math>\geq 6</math> weeks later; the date of progression is the date of the post-treatment scan when <math>\geq 2</math> new lesions were first documented.
 
Progression of soft tissue lesions, as defined per PCWG3 modified RECIST v1.1
 
Death from any cause
 
 
rPFS probability at 6 and 12 months
 

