## Objectives and Corresponding Endpoints (cont.)

Immunogenicity Objective	Corresponding Endpoint
• To evaluate the immune response to atezolizumab	• Incidence of anti-therapeutic antibodies (ATAs) against atezolizumab
Exploratory Immunogenicity Objective	Corresponding Endpoint
• To evaluate potential effects of ATAs	• Relationship between ATA status and efficacy, safety, or PK endpoints

AQA=analgesic quantification algorithm; ATA=anti-therapeutic antibody; CR=complete response; CRPC=castration-resistant prostate cancer; DCR=disease control rate; DOR=duration of response; ECOG=Eastern Cooperative Oncology Group; NCI CTCAE=National Cancer Institute Common Terminology Criteria for Adverse Events; OS=overall survival; PCWG3=Prostate Cancer Working Group 3; PF=physical function; PFS=progression-free survival; PK=pharmacokinetic; PR=partial response; PSA=prostate-specific antigen; rPFS=radiographic progression-free survival; RECIST=Response Evaluation Criteria in Solid Tumors; SSE=symptomatic skeletal event.

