### **Interim Analyses**

A total of two analyses of OS will be performed: one interim analysis and the final analysis.

The interim analysis of the primary endpoint of OS will be performed when approximately 432 deaths have occurred (60% of 720 patients), corresponding to approximately 80% of the 540 deaths required for the final analysis of OS. The required number of deaths for the interim analysis is projected to occur at approximately Month 27 after randomizing the first patient.

The Lan-DeMets alpha-spending function approach will be used to determine the boundary values for statistical significance at the interim and final analysis.

For the primary endpoint of OS, the stopping boundaries will be based on the O'Brien-Fleming alpha-spending function. At both the interim and final OS analysis, key secondary endpoints listed in Section 6.4.2 will be evaluated for statistical significance only if the difference in duration of OS is statistically significant at the appropriate boundary level. For these secondary endpoints, the boundaries for statistical significance will be based on a Pocock alpha-spending function. Key secondary endpoints will be tested at the appropriate significance level in the order specified in Section 6.4.2. If for one endpoint in this list the null hypothesis cannot be rejected, then the results for this and all following endpoints are not statistically significant.

The hierarchical testing procedure with the boundaries determined as described above ensures that the overall type I error for the primary and key secondary endpoints will be controlled at 0.05.

The interim OS analysis will be performed by the iDCC and reviewed by the iDMC. The Sponsor will remain blinded to the results. On the basis of its review of the data, the iDMC will provide a recommendation as to whether to release the study results early because of substantial evidence of efficacy.

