
 
•To evaluate the efficacy of atezolizumab/enzalutamide compared with enzalutamide alone
 
	
 
•OS probability at 12 and 24 months
 
•Time to first SSE An SSE is defined as external beam radiation therapy to relieve skeletal symptoms (including initiation of radium-223 dichloride or other types of radionuclide therapy to treat symptoms of bone metastases), new symptomatic pathologic bone fracture, clinically apparent occurrence of spinal cord compression, or tumor related orthopedic surgical intervention.
 
•rPFS, as assessed by the investigator, and adapted from the PCWG3 criteria (Scher et al. 2016; see Appendix 2). rPFS is defined as the time from randomization to the earliest occurrence of one of the following: A patient is considered to have progressed by bone scan if: The first bone scan with <math>\geq 2</math> new lesions compared to baseline is observed <math>< 12</math> weeks from randomization and is confirmed by a second bone scan taken <math>\geq 6</math> weeks later showing <math>\geq 2</math> additional new lesions (a total of <math>\geq 4</math> new lesions compared to baseline); the date of progression is the date of the first post-treatment scan, OR After the first post-treatment scan, <math>\geq 2</math> new lesions are observed relative to the first post-treatment scan, which is confirmed on a subsequent scan <math>\geq 6</math> weeks later; the date of progression is the date of the post-treatment scan when <math>\geq 2</math> new lesions were first documented.
 
Progression of soft tissue lesions, as defined per PCWG3 modified RECIST v1.1
 
Death from any cause
 

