**Table 1 Objectives and Corresponding Endpoints (cont.)**

Immunogenicity Objective	Corresponding Endpoint
•To evaluate the immune response to atezolizumab	•Incidence of anti-therapeutic antibodies (ATAs) against atezolizumab
Exploratory Immunogenicity Objective	Corresponding Endpoint
•To evaluate potential effects of ATAs	•Relationship between ATA status and efficacy, safety, or PK endpoints

AQA= analgesic quantification algorithm; ATA= anti-therapeutic antibody; CR= complete response; CRPC= castration-resistant prostate cancer; DCR= disease control rate; DOR= duration of response; ECOG= Eastern Cooperative Oncology Group; NCI CTCAE= National Cancer Institute Common Terminology Criteria for Adverse Events; OS= overall survival; PCWG3= Prostate Cancer Working Group 3; PF= physical function; PFS= progression-free survival; PK= pharmacokinetic; PR= partial response; PSA= prostate-specific antigen; rPFS= radiographic progression-free survival; RECIST= Response Evaluation Criteria in Solid Tumors; SSE= symptomatic skeletal event.

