### **3.4.10 Rationale for Patient-Reported Outcome Assessments**

Note: Patient-reported outcome (PRO) assessments are no longer required.

Symptomatic bone metastases are associated with high pain severity, which interferes with patients' ability to function. These two concepts cannot be observed and therefore are best documented through standardized PROs.

In this study, PROs will provide relevant information regarding the treatment effect on prostate cancer-related symptoms and their impact on patients' daily lives. In addition, PROs will also document whether treatment efficacy comes at the expense of patients' quality of life due to deleterious treatment-related symptoms.

Patients will be reporting on very specific symptoms (e.g., pain, fatigue) and their functional impact, which are concepts proximal to patients' experience with the disease and treatment. Although an assessor bias cannot be disregarded in an open-label setting, it is unlikely that this bias would be of such magnitude as to invalidate the data collected through PROs.

Instruments implemented in the study—namely the European Organisation for Research and Treatment of Cancer Quality-of-Life Questionnaire (EORTC QLQ-C30), 10-point pain severity (measured at its worst) numerical rating scale (NRS) selected items from the BPI, the BPI-SF, and the Urinary Scale of the European Organisation for Research and Treatment of Cancer Quality-of-Life Questionnaire Prostate Module (EORTC QLQ-PR-25)—have been selected on the basis of their content validity and performance and to minimize patients' completion burden. These instruments have been previously used in clinical studies in patients with prostate cancer (Logothetis et al. 2012; Fizazi et al. 2014) and have been recommended by PCWG3 (Scher et al. 2016).

The NCI-developed PRO-CTCAE will be used to document the patients' perspective regarding commonly experienced treatment-related symptoms.

In addition, the EQ-5D-5L will be completed to inform pharmacoeconomic models.

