## **6.8 INTERIM ANALYSES**

### **6.8.1 Planned Interim Analyses**

A total of two analyses of OS will be performed: one interim analysis and the final analysis.

The interim analysis of the primary endpoint of OS will be performed when approximately 432 deaths have occurred (60% of 720 patients), corresponding to approximately 80% of the 540 deaths required for the final analysis of OS. The required number of deaths for the interim analysis is projected to occur at approximately Month 27 after randomizing the first patient.

The Lan-DeMets alpha-spending function approach will be used to determine the boundary values for statistical significance at the interim and final analysis (DeMets and Lan 1994).

For the primary endpoint of OS, the stopping boundaries will be based on the O'Brien-Fleming alpha-spending function. At both the interim and final OS analysis, key secondary endpoints listed in Section 6.4.2 will be evaluated for statistical significance only if the difference in duration of OS is statistically significant at the appropriate boundary level. For these secondary endpoints, the boundaries for statistical significance will be based on a Pocock alpha-spending function. Key secondary endpoints will be tested at the appropriate significance level in the order specified in Section 6.4.2. If for one endpoint in this list the null hypothesis cannot be rejected, then the results for this and all following endpoints are not statistically significant.

The hierarchical testing procedure with the boundaries determined as described above ensures that the overall type I error for the primary and key secondary endpoints will be controlled at 0.05 (Hung et al. 2007; Glimm et al. 2010).

The interim OS analysis will be performed by the iDCC and reviewed by the iDMC (see Section 3.2). The Sponsor will remain blinded to the results. On the basis of its review

of the data, the iDMC will provide a recommendation as to whether to release the study results early because of substantial evidence of efficacy.

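### Section 6.4.2 puts pain progression first in the confirmatory sequence after OS, although it is not a listed objective and has no definition, so formal tests of SSE and rPFS depend on it

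*Combined protocol and SAP*

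**What the plan says.** Section 6.4.2 tests OS first and then three key secondary endpoints in fixed order: "Time to cancer-related pain progression", time to first SSE, and rPFS. Once a null hypothesis is not rejected, that endpoint and all later ones count as not significant. Other secondary endpoints are descriptive.

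Section 6.8.1 carries the sequence into both looks: "At both the interim and final OS analysis, key secondary endpoints listed in Section 6.4.2 will be evaluated for statistical significance only if" the OS difference is itself significant at its boundary. The synopsis, under Interim Analyses, has no list of its own and points to the same place: "Key secondary endpoints will be tested at the appropriate significance level in the order specified in Section 6.4.2".

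The objectives are given in the synopsis and again in Table 1. The two secondary lists match and include entries such as "OS probability at 12 and 24 months" and "rPFS probability at 6 and 12 months". SSE and rPFS appear in both with event criteria. Neither the secondary nor the exploratory efficacy list has a pain endpoint.

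On data collection, Section 3.4.10 opens with "Note: Patient-reported outcome (PRO) assessments are no longer required", and Section 4.5.8 carries a note to the same effect.

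**The concern.** The first confirmatory step after OS should be an endpoint that the trial names as an objective and defines well enough to program. Pain progression is neither in the current text. The sequence stops at the first failure, so two endpoints that are named and defined have their formal tests tied to one that is not. If OS were significant, SSE and rPFS could be shut out of confirmatory testing for reasons unrelated to their own results, and a reader of the report could not tell from this document how the deciding pain test was built.

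**Working it through.** The plan gives no power, effect size or expected event count for any key secondary endpoint; its 97% power with 540 deaths concerns OS and is not in dispute. The check is therefore a comparison of sections and a count.

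**The three sequenced endpoints**

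| Order after OS | Endpoint | In synopsis and Table 1 | Event definition | Data collection in the current text |
|---|---|---|---|---|
| 1 | Pain progression | No | None | BPI pain items sit in Section 4.5.8, marked not required; no BPI row in Appendix 1 |
| 2 | First SSE | Yes | Yes | Row in Appendix 1 |
| 3 | rPFS | Yes | Yes | Tumor assessment row in Appendix 1; follow-up after treatment stops is described inconsistently |

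**Counts**

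- Secondary endpoints in Table 1 and the synopsis: OS probability, first SSE, rPFS, rPFS probability, PSA response, time to PSA progression, and objective response = 7; on pain, 0.
- Exploratory efficacy endpoints there: duration of response, disease control, and modified PFS = 3; on pain, 0.
- Key secondary endpoints in Section 6.4.2 absent from Table 1: 1 of 3, the first in order.
- Time-to-event endpoints in Section 6.4.2.1 absent from Table 1: pain progression, immune-modified rPFS, and opiate use = 3 of 6. The last two are outside the tested sequence and so already descriptive: 3 − 2 = 1 affects testing.
- Section 6.4.3 adds two exploratory endpoints that Table 1 does not list separately: time to next systemic therapy and time to unequivocal clinical progression. In all, 3 + 2 = 5 Section 6 endpoints are missing from Table 1, and still only 1 affects testing.
- Appendix 1 rows: 16 + 8 + 5 = 29 over its three pages. Rows for BPI or any other patient-reported instrument: 0. Rows for opiate use: 1.

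**Definition.** As an endpoint of this trial, pain progression appears only as a bare list entry in Sections 6.4.2 and 6.4.2.1, with no instrument, threshold, confirmation rule or handling of opioid use. The one other mention, in Section 1.1.1, concerns a cited cabazitaxel trial.

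**Effect on testing.** For SSE:

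P(SSE tested, pain first) = P(SSE tested, pain removed) × P(pain null rejected | OS null rejected).

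The last factor is not given and cannot be derived, so it lies anywhere from 0 to 1. The chance of testing rPFS, given that OS is rejected, is bounded by the same factor. No numerical loss can be stated.

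**Direction.** In a fixed sequence each step is tested only after the previous rejection. A weak or untestable first step leads to fewer rejections, not more, so type I error is not inflated.

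**The case against.** The strongest reply is that nothing here is shown to fail, and much of it stands.

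- **Untestable?** A reader might infer that the pain test cannot be done. The documents do not show that. BPI data collected before the requirement was dropped may exist, opiate use is still scheduled in Appendix 1, and Section 6.4.2.1 has a general censoring rule. The status of the analgesic log is unsettled: Section 4.4.1 still describes it, but Section 4.5.8 places it among the assessments marked not required.
- **Undefined everywhere?** The protocol refers to a separate SAP that was not supplied, and a definition may stand there or in a previous protocol version. That would answer the missing definition but not the conflict between Section 6.4.2 and Table 1.
- **Truncated pain follow-up?** This is tempting but not established. The notes on patient-reported assessments carry no date, and no data cut-off is given. Nor is rPFS free of the problem: a footnote to Appendix 1 ends study tumor assessments when treatment stops, whereas Sections 3.1 and 4.5.5 continue them.
- **Deleted from Table 1?** The legends expand "AQA=analgesic quantification algorithm" in the synopsis and "AQA= analgesic quantification algorithm" under Table 1, and neither table uses the term. That fits removal of a pain endpoint but does not prove it.
- **Is keeping the order legitimate?** Yes. Holding to a pre-specified sequence after a committee has reviewed comparative data is defensible, so removal is not the only acceptable repair.

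**Conclusion.** The mismatch is real and is confirmed by direct comparison. The first confirmatory step after OS is not a listed objective, is not defined in the supplied text, and probably depends on assessments that are no longer required. Followed as written, the rule makes formal tests of SSE and rPFS conditional on it.

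Severity is minor. The rule can only block claims, and it comes into play only if OS is significant; Section 3.3 records closure for futility on the iDMC's recommendation. A reader might take the finding as evidence of false-positive risk; the structure of the sequence rules that out. The link to the BPI items is an inference, since no section ties the endpoint to an instrument. Confidence is high for the mismatch itself. The documents do not support a conclusion about how much pain data are missing.

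**What to change.** Make the hierarchy in Sections 6.4.2, 6.4.2.1 and 6.8.1 agree with Table 1 and the synopsis.

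- **Default.** Take pain progression out of the confirmatory sequence, leaving OS, then SSE, then rPFS. Report pain progression descriptively on the data collected, citing the definition previously in force. Treat SSE and rPFS as confirmatory under this order only if the sponsor documents that it adopted the order without knowledge of comparative results.
- **If that cannot be documented.** Keep the pre-specified order. Restore pain progression to Table 1 and the synopsis with its pre-existing definition, data source and cut-off, and accept that SSE and rPFS are descriptive if that step fails or cannot be tested.
- **At the same time.** Align the other four Section 6 endpoints missing from Table 1, and reconcile the statements on tumor assessment after treatment stops, since rPFS depends on them.

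The cost is wording in the protocol and SAP plus a dated statement of what the sponsor knew. Under the default the sponsor gives up a confirmatory pain claim. Under either route it may lose confirmatory claims for SSE and rPFS.
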